10.3	Quality Assurance	20
10.4	Adverse Experience Reporting.....	20
11	OTHER ISSUES.....	21
11.1	Health and Disability Ethics Committee Review and Informed Consent.....	21
11.2	Subject Confidentiality	21
11.3	Study Modification/Discontinuation.....	21

12	PUBLICATION OF RESEARCH FINDINGS	21
13	REFERENCES	21
	APPENDIX.....	24
A1.	LETTER OF SUPPORT FOR LEFT VENTRICULAR BIOPSY	24
A2.	SCIENTIFIC STATEMENT ON LV EPICARDIAL BIOPSY – FOR AMENDMENT TO PROJECT LRS-12-01/001	26
A2.1.	Introduction	26
A2.2.	How is an epicardial left ventricular biopsy obtained?	26
A2.3.	What is the indication for epicardial left ventricular biopsy?	26
A2.4.	What are the risks of epicardial left ventricular biopsy?	26
A2.5.	Summary	27
A2.6.	References	27

SYNOPSIS

1.1 **Study Title**

Thiamine to improve stem cell function in patients undergoing bypass surgery: a randomised controlled trial

1.2 **Objectives**

To determine whether high dose oral thiamine administered before coronary artery bypass surgery improves resident cardiac progenitor cell function.

1.3 **Background**

Heart failure is a major cause of morbidity and mortality in New Zealand. Over 10,000 hospital admissions per year are due to heart failure in New Zealand, with a median survival after admission of only 3.5 years, and no reduction in mortality in recent years. There is a large impact on quality of life – the obvious impact on physical health is matched by mental health issues in advanced heart failure comparable to major depression. There are negative effects on other members of the community as well, with family caregivers suffering from emotional distress and impaired health.

Even in mildly symptomatic patients with systolic (pump) dysfunction on optimal treatment, there is a substantial mortality rate. There are still no proven treatments for diastolic (relaxation) dysfunction. Over the past decade, it has become clear that the heart has an intrinsic ability to regenerate itself, orchestrated by progenitor or stem cells. However, cell therapies are still restricted to the research sector, where only modest results have been seen. With the growing epidemic of heart failure, there is an urgent need for new therapies, especially in patients with coronary artery disease.

Patients with diabetes mellitus are at higher risk of developing heart failure compared to those without diabetes. Furthermore we have shown previously that diabetics have reduced resident cardiac progenitor cell number and function, and that this can be improved *in vitro* and *in vivo* (in animal models) using a thiamine analogue. Although the thiamine analogue improved progenitor cell function in cell cultures from both diabetic and non-diabetic animals, the diabetic animals had worse function initially.

1.4 **Design and Outcomes**

This is a single centre, randomised, double-blind, controlled phase 2b trial, built on the infrastructure of an ongoing observational trial. Participants listed for inpatient urgent coronary artery bypass grafting (CABG) will be randomised to thiamine or placebo, for 3-5 days before their procedure. At the time of CABG, the right atrial appendage, which is discarded as a normal part of the procedure, will be collected as well as a small left ventricular biopsy (both of these techniques being a routine part of our current observational study).

The primary outcome is the proliferation ability of resident cardiac progenitor cells, as measured by BrdU activity.

Secondary outcomes are other functional measures, such as the ability to differentiate into cardiomyocytes, as measured by the number of GATA-4 and connexin-43 positive cells after exposure to differentiation medium, and measurement of the level of transketolase to determine the activation of pentose phosphate pathway.

Our primary hypothesis to be tested is that treatment with thiamine will improve the primary outcome in diabetics and non-diabetics. We also wish to test the hypotheses that treatment with thiamine will improve the secondary outcomes in diabetics and non-diabetics, and that diabetics receiving placebo have reduced resident cardiac progenitor cell number and function compared to non-diabetics receiving placebo.

1.5 ***Interventions and Duration***

Patients will be randomised to oral thiamine (2g/day) or matching placebo once listed for inpatient CABG. Total length of time on intervention treatment will be 3-5 days.

1.6 ***Sample Size and Population***

The number of patients to be randomised in total is 40. Randomisation will be stratified based on diabetic status (non-diabetic/diabetic). The study population will be those patients admitted to hospital and awaiting urgent (i.e. inpatient) coronary artery bypass surgery, without valvular heart disease requiring intervention.

2 BACKGROUND

2.1 *Rationale*

Background and need for the study

Heart failure is a major cause of morbidity and mortality in New Zealand. Over 10,000 hospital admissions per year are due to heart failure in New Zealand, with a median survival after admission of only 3.5 years, and no reduction in mortality in recent years.¹ There is a large impact on quality of life – the obvious impact on physical health is matched by mental health issues in advanced heart failure comparable to major depression.² There are negative effects on other members of the community as well, with family caregivers suffering from emotional distress and impaired health.³

Even in mildly symptomatic patients with systolic (pump) dysfunction on optimal treatment, there is a mortality rate of 11% over less than two years.⁴ There are still no proven treatments for diastolic (relaxation) dysfunction. Over the past decade, it has become clear that the heart has an intrinsic ability to regenerate itself, orchestrated by progenitor or stem cells (despite their differences, we use the widely recognised term stem cell interchangeably in those parts of the study likely to read by a wide audience, such as title and abstract).⁵ However, cell therapies are still restricted to the research sector, where only modest results have been seen.⁶ With the growing epidemic of heart failure, there is an urgent need for new therapies, especially in patients with coronary artery disease.

Rationale for patient population chosen

This is a phase 2, randomised control trial with a real-world design. The patient population consists of patients admitted to hospital awaiting urgent in-hospital coronary artery bypass grafting (CABG). In general, these patients have suffered an acute coronary syndrome, and therefore, as patients with the highest grade coronary disease, they have among the highest risks of development of subsequent heart failure. We are stratifying by diabetic status as these patients are at highest risk of developing heart failure⁷ and because our previous studies, described below, have identified these patients as having reduced resident cardiac progenitor cell number and function.

We are excluding those with impaired left ventricular systolic function (ejection fraction < 50%) as these patients are a heterogenous group with potentially widely varying exposures to myocardial ischaemia in the past. Also excluded are those with valve disease severe enough to require intervention at the time of cardiac surgery, as again these are a heterogenous group of patients with different aetiologies of valvular heart disease. We are excluding those below the age of 50 years or having CABG for non-atherosclerotic disease (e.g. coronary dissection) as again patients with these conditions often have additional less common risk factors for coronary disease. Finally those patients already requiring thiamine supplementation or at high risk for requiring thiamine supplementation due to alcohol use will be excluded.

This trial is being built around the framework of an ongoing observational study entitled “Effects of catecholamines on function and signalling in the human diabetic heart”, ethics reference LRS/12/01/001, referred to hereafter as “the observational study”. This study involves collection of atrial appendage and left ventricular tissue

from volunteers undergoing cardiac surgery and has made information delivery, the consent process, and tissue collection relatively routine for a large number of participants undergoing cardiac surgery in Dunedin Hospital. Information about this study is widely available on the cardiology and cardiac surgery wards. In this randomised trial, we will randomise participants to treatment for 3-5 days before surgery, monitor them before and after surgery, but the intra-operative procedures remain those normally followed by the observational study. As described below, the additional risk due to being randomised to active treatment is minimal. In addition, participants who desire to be involved in this randomised trial but do not meet inclusion criteria will be given the opportunity to take part in the observational study.

Rationale for interventional regime chosen

Thiamine is known to be depleted by coronary artery bypass grafting (CABG)⁸ and is also reduced in heart failure.⁹ We wish to determine if short term (3-5 days) treatment with thiamine improves the function of resident cardiac progenitor cells.

The trial is based on our previous research showing that treatment with benfotiamine, a fat-soluble analogue of thiamine, increases the proliferation of resident cardiac progenitor cells (CPCs).¹⁰ In this study, CPCs from animals treated with benfotiamine had an improvement in proliferation of these progenitor cells as measured by the BrdU assay. This was seen in both diabetic and non-diabetic animals, but CPCs from diabetic animals had impaired proliferation ability at baseline. In addition, diabetic animals had lower number of CPCs than non-diabetic animals, and this also improved with benfotiamine. In CPCs isolated from humans, benfotiamine protected CPC proliferation ability when cultured in high glucose medium.

While benfotiamine, a lipid-soluble analogue of thiamine, was used for our pre-clinical studies, this has not been used in high doses in humans before. Although previous studies have not shown any major adverse effects from benfotiamine use even up to a dose of 400mg/day, a report for the European Food Safety Authority concluded that there was insufficient data to demonstrate the safety of benfotiamine as a source of vitamin B1 to be added to food supplements (which is how over the counter vitamins are regulated in the European Union).¹¹ We elected to use oral free thiamine, given its long history of safe use and assessment of toxicity as generally being viewed as “very low”.¹²

We have chosen a “real world” duration of intervention. Approximately 20-50% of coronary artery bypass surgery procedures are performed on patients with an acuity level of “urgent”, where the patient has been admitted to hospital with an acute unscheduled presentation and is to remain in hospital until the procedure is completed. These patients are necessarily higher risk than elective patients, but are generally stable enough to allow a period of 3-5 days of medical intervention prior to surgery. It is during this period, after the patient has been listed for surgery, that consenting patients will be randomised in the trial.

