6.3.3 Medical/Treatment History

Medical history will be obtained by examining the medical record of the patient and discussion with the participant. A standard reporting form will be completed, documenting in particular previous history (especially presence and duration of diabetes), details of current presentation (especially non-ST elevation myocardial infarction vs unstable angina), and relevant tests (especially high sensitivity troponin, HbA1c). Documentation of current medications will be made.

Prior to discharge, brief assessment of development of post-operative complications, such as atrial fibrillation, will be made.

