9.1.2 Secondary outcomes

Secondary outcomes are other functional measures, such as the ability to differentiate into cardiomyocytes, as measured by the number of GATA-4 and connexin-43 positive cells after exposure to differentiation medium, and measurement of the level of transketolase to determine the activation of pentose phosphate pathway

9.2 **Outcomes discussion**

Primary and secondary outcomes will be measured without knowledge of treatment assignment (i.e. blinded).

Bromodeoxyuridine (BrdU) is a thymidine analogue that is taken up by cells actively replicating DNA. As such it is widely used as an assay to determine proliferation of cells, and has appeared in over 20,000 biomedical science articles.¹⁹ In addition, we have demonstrated accuracy in our laboratory, with our animal studies demonstrating

a coefficient of variation of 9% in non-diabetic animals and 13-14% in diabetic animals. As such, it is a valid test to use to assess the function of resident CPCs.

9.3 **Sample Size and Accrual**

The primary outcome will initially be assessed in treated vs non-treated groups (combining diabetics with non-diabetics) and then stratified by diabetic status. We therefore calculated a sample size powered by subgroup (diabetic vs non-diabetic) status. Based on our previous data, with a sample size of 10 in each group (non-diabetic no active treatment, non-diabetic active treatment, diabetic no active treatment, diabetic active treatment) giving a total of 40 patients in total, we will have 99% power and 91% power, in non-diabetics and diabetics respectively, to detect a two-tailed 30% difference in primary outcome with treatment at a significance level of 0.05. Here we use a t-test to compare groups, with data coming from assessment of BrdU activity in CPCs isolated from treated and untreated animals.¹⁰ Note that we may have higher power, as we detected a 79% and 106% increase in mean proliferation activity of stem cells in treated non-diabetic and diabetic animals, respectively, compared with control. However given the uncertainty moving from an animal model to humans, we felt it prudent not to limit groups to less than 10 patients each.

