Accrual rate is expected to be approximately 1-2 participants per fortnight. This is based on current accrual rates of 2-4 participants per fortnight in the observational study – many of these will be eligible for inclusion in this trial and are likely to volunteer based on the low toxicity of the intervention. Given the exclusion of the highest risk cases (those with impaired left ventricular systolic function or those undergoing cardiac surgery on an emergency basis) and the short duration of treatment, we expect the vast majority of those enrolled to complete allocated treatment until CABG, i.e. a low loss to follow-up rate.

9.4 **Data Monitoring**

An interim blinded analysis of the toxicity data will be performed after recruitment of 20 patients by the study team. We expect there to be few adverse experiences on or off active treatment. If more than 20% of participants report adverse experiences, then a separate Data and Safety Monitoring Board will be recruited consisting of at least two clinicians independent of the investigators. These will be supplied with the toxicity data and the unblinding codes, if required. If, in their opinion, excess toxicity is seen with active treatment, a recommendation to halt the trial can be made to the study investigators.

An interim analysis of study recruitment will be made one year after randomisation of the first subject. If recruitment is less than 20 subjects, we will attempt to assess the cause of this slow recruitment. This will be done by comparing with recruitment to the observational study and analysis of screening logs. If study validity can be maintained, an amendment to the study will be made to rectify perceived causes of slow recruitment.

No interim analysis will be made for primary or secondary outcomes given the small number of study participants.

9.5 **Data Analyses**

A standard two-tailed t-test will be used to compare the primary outcome between treated and non-treated groups, using an intention-to-treat analysis. Separate analysis of the primary outcomes stratified by diabetic status will be performed using a t-test. For secondary analyses, differences across multiple groups will be assessed using an analysis of variance (ANOVA) test followed by a Šidák-Holm multiple comparison test. Comparison between two groups will be assessed using t-tests.

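### The primary t-test in Protocol 9.5 leaves out diabetes status, the randomisation stratum that the protocol itself links to lower progenitor-cell proliferation, so between-stratum variation stays in the error

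*Protocol*

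**What the plan says.** - **Primary analysis (Protocol 9.5).** "A standard two-tailed t-test will be used to compare the primary outcome between treated and non-treated groups", by intention to treat, followed by a separate t-test in each diabetes stratum. No baseline variable enters either test.
- **Randomisation (5.3).** Five blocks of four are used in each of the diabetic and non-diabetic strata, which makes 20 patients per stratum.
- **Diabetes and the outcome (2.1).** The choice to stratify rests partly on earlier work finding fewer and less functional progenitor cells in diabetes. Diabetic animals are reported to have had impaired proliferation at baseline.
- **Glucose (2.1).** In cells isolated from humans, "benfotiamine protected CPC proliferation ability when cultured in high glucose medium".
- **Ischaemia (2.1).** Patients with ejection fraction below 50% are excluded because "these patients are a heterogenous group with potentially widely varying exposures to myocardial ischaemia in the past".
- **Baseline record (6.3.3).** The form captures "details of current presentation (especially non-ST elevation myocardial infarction vs unstable angina), and relevant tests (especially high sensitivity troponin, HbA1c".
- **Sample size (9.3).** "with a sample size of 10 in each group", "we will have 99% power and 91% power, in non-diabetics and diabetics respectively, to detect a two-tailed 30% difference in primary outcome with treatment". The inputs are described as "data coming from assessment of BrdU activity in CPCs isolated from treated and untreated animals".

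**The concern.** The protocol identifies diabetes as a factor that lowers the primary outcome and builds it into the randomisation, but drops it from the primary comparison. Blocking within strata balances diabetes between the arms, so the treatment difference is protected from a diabetes shift. The pooled t-test, however, computes its standard error as though that balance had not been imposed. The shift is counted as noise, the interval is wider than it need be, and the test rejects less often than its nominal 5%. In a trial of 40 patients, planned on animal variability and with no pre-treatment BrdU value available (the tissue is obtained only at surgery), precision should not be given away.

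A second, weaker question is whether the recorded HbA1c and presentation could also explain variation within strata.

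**Working it through.** **1. The plan's own figure.** The inputs from 9.2 and 9.3 are 10 v 10, a difference of 0.30 of the control mean, two-sided alpha 0.05, and "a coefficient of variation of 9% in non-diabetic animals and 13-14% in diabetic animals". A two-sample t-test (noncentral t, SD set equal to the CV) gives over 99.9% power at 9% and 99.8% to 99.5% at 13-14%. The stated 99% is consistent with this. The stated 91% is not recovered; it corresponds to an SD of 0.30/1.562 = 0.192 of the control mean, and 99% corresponds to 0.30/2.030 = 0.148. The SD actually used is not printed. These figures concern the stratum t-tests, so the mismatch does not drive this point. On these implied SDs, a shift of 1 SD is about 15% to 19% of the control mean.

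**2. Cost of omitting the stratum.** Let the strata differ by d within-stratum SDs. The protocol gives no human value for d, so a range is assumed. Full blocks split 2:2 put 10 diabetics and 10 non-diabetics in each arm.

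- Sum of squares due to the shift, about each arm mean: 20 × (d/2)² = 5d², so 10d² over both arms.
- Pooled residual mean square, in units of the within-stratum variance: (38 + 10d²)/38 = 1 + 10d²/38.
- Ratio of interval widths, stratum model to pooled test: (2.0262/2.0244)/√(1 + 10d²/38), using t quantiles on 37 and 38 df.
- True type I error of the pooled test: approximately P(|t38| > 2.0244 × √(1 + 10d²/38)).

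| Assumed shift d | Width ratio | Interval narrower by | Pooled type I error |
|---|---|---|---|
| 0 | 1.001 | none | 0.050 |
| 1 | 0.891 | 11% | 0.029 |
| 1.5 | 0.793 | 21% | 0.015 |

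Simulation with 20,000 trials per row gave ratios of 1.001, 0.890 and 0.793. Type I error was 0.051, 0.028 and 0.015 for the pooled test, against 0.050 to 0.052 for the stratum model. With exact balance the two analyses give the same point estimate; only the standard error differs.

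**3. HbA1c and infarction yes/no as further covariates.** R2 is the share of within-stratum variance they explain. The documents do not give it, so a range is assumed. The table shows simulated width ratios (6,000 trials per row; one normal and one binary covariate). The reference is treatment plus stratum at N=40, and treatment alone within one stratum at N=20.

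| R2 | N=40 | N=20 |
|---|---|---|
| 0 | 1.03 | 1.07 |
| 0.05 | 1.00 | 1.04 |
| 0.10 | 0.98 | 1.02 |
| 0.20 | 0.92 | 0.96 |
| 0.30 | 0.86 | 0.90 |

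Break-even is at an R2 of about 5-6% with 40 patients and about 12% with 20. If the covariates are unrelated to the outcome, the interval is about 3% or 7% wider.

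**The case against.** The t-test is valid under randomisation: it is unbiased and, if anything, conservative. The protocol also runs a t-test within each stratum, which removes the diabetes shift completely, and the sample size was set on those tests. If the animal variability carried over to humans, the pooled comparison would have ample power without adjustment. All of this stands, and it makes the point one of efficiency. It does not justify the pooled test as primary. The stratum tests have only 10 v 10, the protocol itself admits uncertainty in moving from animals to humans, and the stratum term is essentially free. Supportive analyses may sit in an SAP that is not shown, but 9.5 itself fixes the primary test.

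Three stronger readings are tempting and are not supported.

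- A reader might infer that the protocol regards ischaemic exposure as a source of variation in progenitor-cell function. The sentence in 2.1 explains an exclusion, describes patients who are not randomised, and does not mention these cells. The glucose finding is in vitro. Nowhere does the protocol say that HbA1c, troponin or infarct type predicts BrdU activity within a stratum.
- A reader might infer that a chance imbalance in infarction, such as 7 v 3, distorts the estimate. Such imbalance is random error already reflected in the standard error, and it matters only if infarction affects BrdU.
- A reader might infer that these covariates are the only way to gain precision. The stratum term is another, and the better supported.

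**Conclusion.** The point holds for the stratification factor. The primary analysis ignores a variable that the design balances and that the protocol links to the outcome. The loss is nil with no shift, and the stratum model's interval is about 11% or 21% narrower for an assumed shift of 1 or 1.5 SD. This rests on equal strata of 20, complete blocks and a common within-stratum SD; the size of the human shift is unknown. The case for HbA1c and presentation is weaker. With 40 patients they may help or cost a little, and in the 10 v 10 stratum tests they would widen the interval unless R2 exceeds about 12%. That supports a pre-named supportive analysis, not a change to the primary one. The plan contains no bias or invalid test on this point.

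**What to change.** - **9.5, primary:** make the primary estimate the treatment coefficient, with its 95% confidence interval, from a linear model with treatment and diabetes stratum, by intention to treat. Leave the two stratum t-tests unadjusted.
- **9.5, supportive:** pre-name baseline HbA1c and presentation (infarction yes/no) as added covariates in a supportive analysis of the 40-patient comparison only, fixed before unblinding.
- **6.2.2:** for that analysis to be complete, state that HbA1c will be measured on the baseline blood where no clinical value exists; at present this is only permitted.

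**Cost:** a change of wording, one degree of freedom in the primary model, and an HbA1c assay on blood already drawn for some patients. The supportive interval would be about 3% wider if the covariates prove unrelated to the outcome. Sample size and trial conduct do not change.
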